6.6.3. Permitted Inflammatory Bowel Disease Medications and Rescue Medications

Permitted concomitant treatment for UC and CD must remain at a stable dose (no increase or decrease) during the study treatment period (except for decreases due to adverse events); if doses are increased, patients must be withdrawn from the study. The dose of any background medication for UC and CD should not be changed during the screening and double-blind treatment period. If a patient requires initiation of a new therapy for UC or CD, the patient should be withdrawn from the study, and appropriate treatment should be administered at the discretion of the investigator.

Patients will be allowed to use the following medications as detailed below:

- Concomitant use of oral 5-ASA or sulfasalazine. Dose must be stable for at least 4 weeks prior to endoscopy and through week 14. If oral 5-ASA treatment has been recently discontinued, it must have been stopped for at least 2 weeks prior to endoscopy.
- A stable dose of oral corticosteroids (prednisone equivalent of up to 20 mg/day; budesonide of up to 9 mg/day) for at least 2 weeks prior to endoscopy and through week 14. If oral corticosteroids have been recently discontinued, they must have been stopped at least 2 weeks prior to endoscopy. Decreases in steroid use due to adverse events are allowed.
- A stable dose of immunosuppressant drugs (methotrexate, 6-MP, or AZA consistent with regional standard of care) for 4 weeks prior to endoscopy and through week 14. Decreases due to adverse events are permitted.

Following the week 14 visit if not continuing on to the long-term extension study, patients will no longer need to abstain from the medications that were prohibited or required no change in dose during the screening and induction period. Biologic treatment(s) should not be initiated during the follow-up period without discussion with the sponsor.

6.6.4. Prohibited Medications and Therapies

The following medications will be prohibited during this study:

- Any live (attenuated) vaccines from 14 days prior to the first screening visit and throughout the study.
- Topical (rectal) treatment of 5-ASA or intravenous, intramuscular (parenteral), or enema/suppository administration of corticosteroids within 2 weeks prior to endoscopy through week 14.
- Prednisone dose of >20 mg/day or equivalent oral systemic corticosteroid from 2 weeks prior to endoscopy through week 14.
- The patient is currently using any systemic immunosuppressant or immunomodulatory biologic or nonbiologic (other than those listed in inclusion criterion “h” and those that are used for IBD) within 30 days or 5 half-lives (whichever is longer) prior to the endoscopy.
- Biologics including anti-TNF, anti-integrins, anti-IL-12/23, or anti-IL-23 within 3 half-lives prior to randomization.
- Small molecules including JAK inhibitors, or S1P receptor modulators, within 5 half-lives or shorter washout duration if undetectable drug levels can be demonstrated prior to randomization.
- Oral budesonide of >9 mg/day or equivalent from 2 weeks prior to endoscopy through week 14.
- Patients requiring a surgical intervention for UC or CD will be discontinued from the study

6.7. Procedures for Monitoring Patient Compliance

The investigator will be responsible for monitoring patient compliance with this protocol from the start of the screening period through the EOS visit.

If the investigator or the sponsor determines that the patient is not in compliance with the study protocol, the investigator and the sponsor should determine whether the patient should be withdrawn from the study (Section 5.3). The Independent Ethics Committee (IEC)/IRB/competent authorities should be notified if required by local regulation.

6.8. Randomization and Blinding

This is a randomized, double-blind, placebo-controlled study. Patients who meet all the inclusion criteria and none of the exclusion criteria will be randomly assigned to receive TEV-48574 (single loading dose/6 induction doses): 2250/900 mg, 2250/450 mg, or placebo to match TEV-48574, in a 1:1:1 ratio, stratified by diagnosis (UC or CD) and previous exposure to advanced therapy for IBD (yes/no) (biologics, JAK inhibitors, and S1P receptor modulators).

Prior to Amendment 03 with Revision 01, patients were randomly assigned to receive 1 of 4 treatment regimens (2250/1800 mg, 2250/900 mg, 2250/450 mg, or placebo to match TEV-48574); these patients will continue to receive the same dose, volume, and rate of administration of the IMP to which they were initially randomized and will remain blinded.

Approximately 120 UC patients and 120 CD patients will be randomly assigned to the treatment groups by means of a computer-generated randomization list using interactive-response technology. The specifications for randomization will be under the responsibility and oversight of Teva Global Statistics.

The randomization list will be assigned to the relevant treatment groups through a qualified service provider, eg, via the Randomization and Trial Supply Management (RTSM) system. The generation of the randomization list and management of the RTSM system will be done by a qualified service provider under the oversight of the responsible function at Teva.

6.9. Maintenance of Randomization and Blinding

6.9.1. Maintenance of Randomization

Patient randomization codes will be securely maintained by the service provider contracted to generate the codes. At the time of analysis (interim analysis and after the end of study), after receiving unblinding request from Teva statistician, the service provider will provide the unblinded IMP assignment according to the processes defined in the relevant Standard Operating Procedure (SOP).

6.9.2. Blinding and Unblinding

Personnel who may be aware of IMP assignments will not be involved in the conduct of any study procedures or assessment of any adverse events.

The patients and the site will be blinded until all patients complete the study, and the database is locked for final analysis for both indications. The sponsor study team will be blinded to treatment assignment until the database is locked for analysis of each indication.

Details regarding unblinding of an independent Teva team while maintaining the blind of the study, in case the final analysis is conducted for one indication while the other indication is ongoing, will be provided in a separate unblinding charter.

Pharmacokinetic, PD and immunogenicity samples will be collected for bioanalysis during the study. Individuals responsible for sample bioanalysis and other responsible personnel may know who received test IMP and who received placebo IMP during the study. Personnel responsible for bioanalysis will be provided with the randomization code to facilitate the analysis. However, the personnel responsible for bioanalysis will not have access to clinical safety and efficacy data and will provide concentration data to other personnel in a manner that will not identify individual patients (ie, a dummy patient identifier will be linked to the concentration data of an individual patient).

In case of a serious adverse event, pregnancy, or in cases when knowledge of the IMP assignment is needed to make treatment decisions, the investigator may unblind the patient's IMP assignment as deemed necessary, mainly in emergency situations. Individual randomization codes, indicating the IMP assignment for each randomized patient, will be available to the investigator(s) or pharmacist(s) at the investigational center via the RTSM, both via telephone and internet. Breaking of the treatment code can always be performed by the investigator without prior approval by the sponsor; however, the sponsor should be notified following the breaking of the treatment code. The patient's IMP assignment should not be revealed to the sponsor.

When a blind is broken, the patient will be withdrawn from the study, and the event will be recorded on the CRF. The circumstances leading to the breaking of the code should be fully documented in the investigator's study files and in the patient's source documentation.

Assignment of IMP should not be recorded in any study documents or source document.

For an adverse event defined as a suspected unexpected serious adverse reaction (SUSAR) (ie, reasonable possibility; see Section 8.1.6), Global Patient Safety and Pharmacovigilance (GPSP) may independently request that the blind code be broken (on a case-by-case basis) to comply with regulatory requirements. The report will be provided in an unblinded manner for regulatory submission. If this occurs, blinding will be maintained for the investigator and for other personnel involved in the conduct of the study, and analysis and reporting of the data.

Interim analyses as described in Section 10.13 will be performed throughout the study by unblinded analysis groups external to Teva and will be reviewed by an IDMC.

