4.4. Stopping Rules for the Study

4.4.1. Individual Stopping Criteria

4.4.1.1. Permanent Individual Withdrawn from IMP

IMP will be discontinued in the event of any of the following:

- The patient develops a serious or severe infection that is:
 - Life threatening

- Requires intensive care unit admission
 - Systemic opportunistic infection including tuberculosis (including pulmonary), cytomegalovirus (CMV; including CMV colitis), and listeriosis
- The patient experiences a serious or severe hypersensitivity reaction following investigational medicinal product (IMP) administration, meeting the Common Terminology Criteria for Adverse Events (CTCAE) criteria 3 to 4:
 - Anaphylaxis
 - Allergic reaction
 - Serum sickness
- The patient experiences a serious or severe Cytokine Release Syndrome following IMP administration, defined as CTCAE grade 3 to 4.
- The patient is diagnosed with malignant neoplasm other than appropriately treated basal cell carcinoma or squamous cell carcinoma of the skin or in situ carcinoma of uterine cervix.
- The patient experiences a serious adverse event where in the investigator, after consultation with the study sponsor's medical expert, assesses there is a reasonable possibility that the serious adverse event may be caused by the IMP.
- The patient becomes pregnant (see Section 8.3).
- The patient requires prohibited medications or an increase from baseline of the medications for the treatment of UC and CD, including surgery for UC and CD (see Section 6.6.3 and Section 6.6.4).
- Neutrophil count of:
 - Absolute neutrophil count $<0.5 \times 10^9/L$ confirmed on repeat testing within 3 to 5 days
 - Absolute neutrophil count $<1.0 \times 10^9/L$ that lasts for 2 weeks (retested every 3 to 5 days) or accompanied by fever $\geq 38.5^\circ\text{C}$
- Lymphocyte count:
 - Lymphocyte count $<0.2 \times 10^9/L$ confirmed on repeat testing within 3 to 5 days
 - Lymphocyte count 0.2 to $0.5 \times 10^9/L$ that lasts for 2 weeks (retested every 3 to 5 days)
- Hemoglobin $<8 \text{ g/dL}$ or an absolute decrease of $\geq 3 \text{ g/dL}$ from baseline (confirmed in repeated test)
- Platelets $<50 \times 10^9/L$ (confirmed in repeated test)
- Liver Chemistry Stopping and Increased monitoring criteria
 - (Refer to Liver Safety Required Actions and Follow up Assessments section in [Appendix K](#))

- alanine aminotransferase (ALT) or aspartate aminotransferase (AST) $\geq 5x$ upper limit of normal (ULN)

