- k. Current or history of chronic liver or biliary disease (with the exception of Gilbert's syndrome, asymptomatic gallstones or uncomplicated fatty liver disease) at screening or baseline ALT or AST $>2\times$ ULN or bilirubin $>1.5\times$ ULN (isolated bilirubin $>1.5\times$ ULN is acceptable if bilirubin is fractionated and direct bilirubin $<35\%$) at screening.
- l. Absolute neutrophil count $<1.5\times 10^9/L$ or Hemoglobin $<9\text{ g/dL}$ or lymphocyte count $<0.8\times 10^9/L$ or platelet count $<100,000/\text{mL}$
- m. The patient has QTc $>480\text{ ms}$
- n. Any acute infection which in the opinion of the investigator compromises the safety of the patient.
- o. The patient is currently pregnant or lactating or is planning to become pregnant or to lactate during the study or for at least 50 days after administration of the last dose of IMP in case of early termination. Any woman becoming pregnant during the study will be withdrawn from the study.
- p. The patient has a known hypersensitivity to the IMP and/or excipients.
- q. Presence of a transplanted organ.
- r. A history of malignancy within the last 5 years (exception: basal cell carcinoma or in situ carcinoma of the cervix if successful curative therapy occurred at least 12 months prior to screening or curatively resected papillary thyroid cancer).
- s. Patient is receiving any of the following therapies within the designated time period:
 - The patient is currently using any systemic immunosuppressant or immunomodulatory biologic or nonbiologic (other than those listed in inclusion criterion "h" and those that are used for IBD) within 30 days or 5 half-lives (whichever is longer) prior to the endoscopy.
 - $>9\text{ mg/day}$ of oral budesonide or $>20\text{ mg/day}$ prednisone or equivalent within 2 weeks prior to the endoscopy.
 - Topical (rectal) treatment of 5-ASA or intravenous, intramuscular (parenteral), or enema/suppository administration of corticosteroids within 2 weeks prior to the endoscopy.
 - Biologics including anti-TNF, anti-integrins, anti-IL-12/23, or anti-IL-23 within 3 half-lives prior to randomization.
 - Small molecules including JAK inhibitors, or S1P receptor modulators, within 5 half-lives or shorter washout duration if undetectable drug levels can be demonstrated prior to randomization.
 - Other investigational procedures or products, within 30 days or 5 half-lives of investigational product prior to the endoscopy, whichever is longer.

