5.3. Withdrawal Criteria and Assessments/Procedures for the Patient

In accordance with the Declaration of Helsinki (in accordance with the applicable country's acceptance), patients may completely withdraw from the study (ie, with no further study participation or contact) at any time for any reason. Patients may also discontinue IMP and remain in the study for assessments after consultation with the investigator and/or sponsor. The investigator and/or sponsor may also discontinue a patient from IMP and/or withdraw a patient from the study in any of the following events:

- in the event of intercurrent illness, adverse events, pregnancy, or any other reason concerning the health or well-being of the patient that indicates to the investigator that continued participation is not in the best interest of the patient (see also Individual Stopping Rules can be found in Section 4.4.1);
- if the patient is noncompliant with the study procedures and assessments or protocol-defined study restrictions or prohibited concomitant medication

Patients who terminate the study should complete the safety and efficacy evaluations specified for early termination in the Study Procedures and Assessments schedule ([Table 1](#)) at the time they terminate study participation, and they will be encouraged to complete the follow-up period in the study.

Investigators are to discuss patients who may be considering discontinuing IMP or withdrawing completely from the study with the sponsor as soon as the site becomes aware of the situation.

Investigators should attempt to obtain information on patients in the case of withdrawal from the study or discontinuation from IMP. Results of any evaluations and observations, together with a narrative describing the reason(s) for withdrawal from the study or discontinuation from IMP, should be recorded in the source documents. The CRF should document the primary reason for withdrawal from the study or discontinuation from IMP.

See [Appendix E](#) for information regarding how the study will define and address lost to follow-up patients to help limit the amount and impact of missing data.

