8.3. Pregnancy

Any female patient becoming pregnant during the screening period will be considered a screen failure and will not be allowed to rescreen.

Any female patient becoming pregnant during the study will discontinue IMP.

All pregnancies of women participating in the study and female partners of men participating in the study, if applicable, that occur during the study, or within 5 half-lives (50 days) of the last IMP administration, are to be reported immediately to the individual identified in the Clinical Study Personnel Contact Information section of this protocol, and the investigator must provide the sponsor (LSO/CRO) with the completed pregnancy form. The process for reporting a pregnancy is the same as that for reporting a serious adverse event but using the pregnancy form ([Section 8.1.8](#)).

All female patients and female partners of men participating in the study (female partners of men participating in the study who become pregnant will be asked to sign an ICF) who become pregnant will be monitored for the outcome of the pregnancy (including spontaneous, elective, or voluntary abortion). If the pregnancy continues to term, the outcome (health of the infant up to 8 weeks of age), including details of birth and presence or absence of any birth defect, congenital abnormalities, or maternal and newborn complications, will be reported to the sponsor. Any

complication of pregnancy during the study and any complication of pregnancy that the investigator becomes aware of after withdrawal from the study will be reported as an adverse event or serious adverse event, as appropriate.

If the pregnancy in the woman participating in the study and/or the female partners of men participating in the study does not continue to term, 1 of the following actions will be taken:

- For a spontaneous abortion, report as a serious adverse event (in addition to the pregnancy form).
- For an elective abortion due to developmental anomalies, report as a serious adverse event (in addition to the pregnancy form).
- For an elective abortion **not** due to developmental anomalies, report on the pregnancy form; do not report as an adverse event.

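### Pregnancy and investigator code breaks lead to study withdrawal (5.2(o), 6.9.2), which makes the week 18 safety visit optional; the sections on pregnancy also disagree

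*Protocol*

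**What the plan says.** **Pregnancy.** Four sections deal with a woman who becomes pregnant during the study.

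- 5.2, criterion o: "Any woman becoming pregnant during the study will be withdrawn from the study".
- 4.4.1.1 lists pregnancy among the events that permanently stop IMP and does not mention study status.
- 8.3: "Any female patient becoming pregnant during the study will discontinue IMP".
- 5.3 includes pregnancy in a list where the investigator or sponsor "may also discontinue a patient from IMP and/or withdraw a patient from the study in any of the following events".

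Section 5.3 also separates stopping drug from leaving the study: "Patients may also discontinue IMP and remain in the study for assessments after consultation with the investigator and/or sponsor".

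**Code break.** Section 6.9.2 allows the investigator to unblind "In case of a serious adverse event, pregnancy, or in cases when knowledge of the IMP assignment is needed to make treatment decisions". The consequence is: "When a blind is broken, the patient will be withdrawn from the study, and the event will be recorded on the CRF". No exception is given. The section's first sentence keeps anyone who knows an assignment away from study procedures and adverse event assessment.

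**After withdrawal.** Under 4.1 and 5.3 the patient has the early termination assessments and is encouraged, not required, to complete the follow-up period. Appendix A (item 4) makes the early termination visit the same as visit 8. Section 8.1.3 ends adverse event recording at the patient's last visit.

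**The concern.** There are two separate matters.

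First, sites have inconsistent instructions on pregnancy. One section requires study withdrawal, two require only that drug stops, and one leaves the choice open. A site that keeps the woman under observation acts within 5.3 and 8.3 but departs from 5.2(o).

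Second, the code-break rule takes out of scheduled follow-up a group selected by a serious adverse event, a pregnancy or an urgent treatment decision. Their later safety data are of particular interest.

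At stake is post-treatment information on new adverse events, laboratory values, ADA and drug level. Withdrawal gains nothing for efficacy: stopping treatment for any reason is already non-response (3.2), and so is a missing week 14 evaluation (10.3.1).

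**Working it through.** The protocol gives no figure to reproduce here. The check compares the sections and counts visits in Table 1.

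**1. Do the pregnancy sections conflict?** Stopping IMP and then withdrawing the patient satisfies all four. Stopping IMP and keeping her in the study satisfies 4.4.1.1, 8.3 and 5.3 but not 5.2(o). The sections therefore disagree on whether withdrawal is required, although one course complies with all of them.

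**2. What changes on withdrawal?** The right comparator is what the protocol prescribes elsewhere after permanent discontinuation for a safety reason. Appendix K does this for liver events: the early termination assessments and the follow-up period, with no softening to encouragement.

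| Contact | Appendix K (liver event) | Withdrawn under 5.2(o) or 6.9.2 |
|---|---|---|
| Early termination visit | to be completed | to be completed |
| Week 18 follow-up | to be completed | encouraged only |

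The difference is 2 − 1 = 1 visit, and 0 if the patient attends anyway. Table 1 places adverse event review, clinical laboratory tests, ADA and drug level at week 18. The ADA and drug-level loss applies only to active-arm patients, because placebo samples are not analysed (9.1, 9.3).

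**3. When can active recording of new events end?** Inputs are the nominal days in Table 1: last dose day 85, visit 8 day 99, follow-up day 127. Assume dosing on schedule, early termination within one dosing interval, and no allowance for the ±3-day window.

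- Early termination without follow-up: 0 to 99 − 85 = 14 days after the last dose.
- Completer who attends follow-up: 127 − 85 = 42 days after the last dose.

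**4. Does the later time point carry information?** The first-in-human study (2.2.2.1.3) suggests that it can. Of three ADA-positive patients in the repeat-dose part, two were positive only about 7 weeks after the last dose. One subject given a single 1000 mg dose had a transient low-titre response 43 days after dosing. A sample at 0 to 14 days could miss such responses. The two late repeat-dose cases were in the 200 mg cohort, below the doses used here, so this shows that late ADA occurs but does not give its expected frequency. ADA at the follow-up visit is part of a secondary endpoint (3.1).

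**5. What remains in place?**

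- An adverse event that causes discontinuation or withdrawal is monitored to resolution, stabilisation, referral or an unrelated cause (5.3, 8.1.3).
- Pregnancies are reported during the study "or within 5 half-lives (50 days) of the last IMP administration", and their outcome is followed (8.3).
- Serious events after the patient's last visit are reported if the investigator hears of them (8.1.7, 8.1.8.1).

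What becomes optional is the active search for new events, together with the week 18 samples.

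**The case against.** The case on the other side is that the code-break rule is a defensible choice. The first sentence of 6.9.2 bars unblinded staff from assessing adverse events, and an investigator who breaks a code falls under that bar. Keeping the patient in the study means accepting some unblinded assessments. On pregnancy, 4.4.1.1 is only a list of reasons to stop drug, and 8.3 itself provides for complications learned of after withdrawal, so 8.3 is compatible with 5.2(o). Much of this stands: 6.9.2 contains a poor rule rather than a contradiction, and the pregnancy conflict is modest. The blinding argument is weaker than it looks. Read literally, the same sentence would stop the investigator from following the index event, which 5.3 and 8.1.3 require, so it needs a clarifying clause in any case.

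A reader might infer more than the documents support in four ways.

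- **Many visits lost.** For a code break at week 2, Table 1 still holds 7 adverse event visits, 5 laboratory visits and 4 ADA and drug-level samplings. Subtracting one each for early termination leaves 6, 4 and 3. These counts assume that a patient off drug would attend every remaining visit, which 5.3 permits but does not require.
- **A shortfall against 50 days.** The 50-day period in 8.3 governs pregnancy reporting and does not depend on remaining in the study. Subtracting visit timing from it measures no lost obligation.
- **Every unblinding triggers withdrawal.** When pharmacovigilance unblinds for a SUSAR, 6.9.2 keeps the investigator blinded and states no withdrawal. The rule is best read as covering investigator code breaks only.
- **Week 18 is otherwise universal.** Completers who enter the extension study skip it too (4.1), although they move into another study.

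**Conclusion.** The point holds as an inexpensive improvement to safety follow-up and a needed alignment of the pregnancy wording. The size is one visit per affected patient: week 18 moves from scheduled to encouraged, and active recording of new events may end 0 to 14 days after the last dose instead of 42. This rests on on-schedule dosing, prompt early termination, a patient who declines the encouraged visit, and the Appendix K pathway as comparator. The protocol gives no expected number of code breaks or pregnancies, so no study-level total can be stated. The primary estimand is unaffected. The change should be made, but the trial's conclusions do not depend on it.

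**What to change.** - In 5.2(o), and in 6.9.2 for investigator code breaks only (not SUSAR unblinding), replace study withdrawal with permanent discontinuation of IMP. Unless consent is withdrawn, the patient then completes the early termination assessments and the week 18 safety follow-up visit, as Appendix K prescribes for liver events.
- Align 5.3 and 8.3 with that wording.
- Exempt pregnant patients from study endoscopy and biopsy unless clinically indicated. The early termination visit currently includes both, with no such exemption.
- Add a clause to the first sentence of 6.9.2 allowing the unblinded investigator to carry out that patient's safety follow-up, and flag on the CRF any adverse event assessed after the code break.

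The cost is wording in four sections, one CRF flag and approval with the next amendment. No new visit type is needed. The downside is that a few adverse event assessments will be made unblinded; the flag lets them be identified in the analysis.
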